EU	European Union
F	female
FDA	Food and Drug Administration
FSH	follicle-stimulating hormone
FU	follow-up
GCP	Good Clinical Practices
GGT	gamma-glutamyl transferase
GH	growth hormone
GMP	Good Manufacturing Practices
HbA1c	glycosylated hemoglobin
HBV	hepatitis B virus
HCV	hepatitis C virus
HIV	human immunodeficiency virus
HQ-CT	Hyperphagia Questionnaire for Clinical Trials
HR	heart rate
ICF	Informed Consent Form
ICH	International Conference on Harmonisation
IEC	Institutional Ethics Committee
INR	international normalized ratio
IP	Investigational Product
IRB	Institutional Review Board
ISF	Investigator Site File
ITT	intent-to-treat

Acronym	Definition
IUD	intrauterine device
IUS	intrauterine hormone-releasing system
LTE	long-term extension
M	male
MCT	medium chain triglycerides
MCH	mean corpuscular hemoglobin
MCHC	mean corpuscular hemoglobin concentration
MCV	mean corpuscular volume
mITT	modified intent-to-treat
MMRM	mixed model for repeated measures
nCLB	norclobazam
NOAEL	no-observed-adverse-effect-level
QTcF	QT interval corrected with Fridericia's Formula
PCP	phencyclidine
PK	pharmacokinetic
PP	per protocol
PPAR γ	peroxisome proliferator-activated receptor γ
PT	prothrombin time
PWS	Prader-Willi Syndrome
RAND	randomization
RBC	red blood cells
RDW	red cell distribution width
RR	respiratory rate
SAE	serious adverse event
SAP	Statistical Analysis Plan
SD	standard deviation
SOC	System Organ Class
SOP	standard operating procedures
SUSAR	suspected unexpected serious adverse reaction
T _{1/2}	half-life
T _{max}	time to maximal concentration
TBD	to be determined

Acronym	Definition
TEAE	treatment-emergent adverse event
THC	tetrahydrocannabinol
TMF	Trial Master File
UGT	5'-diphospho-glucuronosyltransferase
ULN	upper limit of normal
US	United States
W	week
WBC	white blood cells
WOCBP	women of childbearing potential

2. SYNOPSIS

Name of Sponsor/Company: Radius Pharmaceuticals, Inc. (Radius)
Name of Finished Drug: RAD011 (Cannabidiol Oral Solution) 100 mg/mL
Name of Active Ingredient: Cannabidiol (CBD)
Title of Study: A Phase 2/3, Randomized, Double-Blind, Placebo Controlled Study of RAD011 (Cannabidiol Oral Solution) for the Treatment of Patients with Prader-Willi Syndrome
Phase of Development: Phase 2/3
Study Center(s): Approximately 38 sites (20 NA, 18 non-NA)
Number of Patients Randomized (Planned): Ages 12 to 65 years (Phases 2 and 3): ~191 patients Ages 8 to <12 years (Phase 3): ~30 patients
Objective: The primary objective of the Phase 2 part of this study is to assess the safety and tolerability of multiple doses levels of RAD011 in order to select 1 or 2 dose level(s) to further evaluate in the Phase 3 part of the study. The primary objective of the Phase 3 part of this study is to assess the effect of RAD011 on hyperphagia-related behavior in patients with Prader-Willi Syndrome (PWS).
Design and Methodology: This is a seamless Phase 2/3, double-blind, randomized, placebo-controlled clinical study in patients diagnosed with PWS. Following consent (or legal guardian consent and patient assent as appropriate), patients will be screened for eligibility to participate in this study. The study will consist of six similar periods for the Phase 2 and Phase 3 parts of the study: 
 1. Screening Period (3 weeks) 
 a. Review of eligibility prior to proceeding to the Tolerability Period 2. Tolerability Period (6 weeks) 
 a. Determination of randomization eligibility [†] 3. Dose Escalation Period (3 weeks) 4. Maintenance Period (24 weeks)[‡] 5. Taper Period (2 weeks)[‡] 6. Follow-Up Period (2 weeks)[‡]. 
[†]Patients who do not meet criteria for randomization eligibility will not be randomized to study SCOUT-015.
 
[‡]All patients participating in the Maintenance Period may be offered participation in the long-term extension study (SCOUT-016). Patients who do not enroll in the SCOUT-016 study will have their investigational product (RAD011 or placebo [IP]) tapered off over 2 weeks (14 days), followed by a 2-week (14-day) safety follow-up.
 
After approximately 45 patients complete 4 weeks of the Maintenance Period of the Phase 2 part of the study, the Data Monitoring Committee (DMC) will meet to review safety and tolerability data and to recommend 1 or 2 RAD011 dose level(s) for evaluation in the Phase 3 part of the study.
 
Screening Period (3 weeks, Visit 1 [Weeks -3 to 0]):
 
Phase 2 and Phase 3 Parts of the study
 
All patients with a signed informed consent/assent will undergo Screening assessments. Screening assessments will include a full medical history and physical exam, a review of documentation of PWS

diagnosis, an electrocardiogram (ECG), laboratory and questionnaire assessments (including the HQ-CT). To be eligible for the Tolerability Period, patients must meet the following criterion:

- Mean HQ-CT score ≥ 13

Patients not meeting Inclusion/Exclusion criteria for entry in the study will not be eligible for the study and may not be screened again. Caregivers will be required to either assist the patient or complete the questionnaires on behalf of the patient. The same caregiver should be available throughout the study to help in completing the questionnaires for purposes of consistency.

Tolerability Period (6 weeks, Visits 2 to 5 [Weeks 1 to 7])

Phase 2 and Phase 3 of the study

Patients who meet the eligibility criteria will undergo a 6-week Tolerability Period. During this Period, all patients will receive placebo at a dose of 0.1 mL/kg/day to assess tolerability of the formulation without active CBD and give patients time to adjust to study procedures and future IP administration. Patients unable to tolerate the 0.1 mL/kg/day dose level will be withdrawn from the study.

Patients/caregivers will also complete serial HQ-CT questionnaires at 2-week intervals. At the end of the 6-week Tolerability Period and prior to randomization, patient randomization eligibility based on tolerability and HQ-CT scores will be evaluated. To be eligible for randomization, patients must meet both of the following criteria:

- Mean HQ-CT score ≥ 13 obtained from prior HQ-CT scores
- Decrease from the Tolerability Period to the Screening Period in HQ-CT score ≤ 7 points

Patients who do not meet criteria for randomization eligibility will not be randomized to study SCOUT-015.

Randomization (Visit 5 [Week 7])

Phase 2 of the study

Following the Tolerability Period, patients meeting randomization eligibility criteria will be randomized to 1 of 6 groups (3 active and 3 placebo with the ratio of 2:2:2:1:1:1): low dose (10 mg/kg/day [0.1 mL/kg/day]) RAD011, mid dose (20 mg/kg/day [0.2 mL/kg/day]) RAD011, high dose (40 mg/kg/day [0.4 mL/kg/day]) RAD011, low volume (0.1 mL/kg/day) placebo, mid volume (0.2 mL/kg/day) placebo, or high volume (0.4 mL/kg/day) placebo divided twice daily.

Phase 3 of the study

Following review of the Phase 2 safety and tolerability data by the DMC, 1 or 2 dose level(s) will be recommended for further development and assessment in the Phase 3 part of the study.

Dose Escalation Period (3 weeks, Visits 5 to 7 [Weeks 7 to 9])

Phase 2 of the study

After completing the Screening and Tolerability Periods, all randomized patients will be initiated on the IP 10 mg/kg/day (0.1 mL/kg/day) for a period of 1 week at Visit 5 (Week 7). Patients randomized to low dose or low volume IP (10 mg/kg/day) will continue at a dose of 10 mg/kg/day (0.1 mL/kg/day) until the end of Visit 7 (Week 9). Patients randomized to mid dose or mid volume IP (20 mg/kg/day) will have their dose increased to 20 mg/kg/day (0.2 mL/kg/day) at Visit 6 (Week 8) and will continue at that dose until the end of Visit 7 (Week 9). Patients randomized to high dose or high volume IP (40 mg/kg/day) will have their dose increased to 20 mg/kg/day (0.2 mL/kg/day) at Visit 6 (Week 8) and to 40 mg/kg/day (0.4 mL/kg/day) at Visit 7 (Week 9).

The Investigator, or designee, will contact patients/caregivers by phone call, video call, email, or other remote means of communication at Visits 6 (Week 8) and 7 (Week 9) to determine if the patient's dose may be escalated to the next dose level. Dose reductions will not be allowed during the Dose Escalation Period. Patients unable to tolerate their assigned dose level(s) during the Dose Escalation Period will be withdrawn from the study.

Phase 3 of the study

After completing the Screening and Tolerability Periods, all patients will be initiated on 10 mg/kg/day IP (0.1 mL/kg/day) for a period of 1 week at Visit 5 (Week 7). Dose escalation will occur as in the Phase 2 of the study, according to the DMC-recommended Phase 3 dose level(s).

The Investigator, or designee, will contact patients/caregivers by phone call, video call, email, or other remote means of communication at Visits 6 (Week 8) and 7 (Week 9) to determine if the patient's dose may be escalated to the next dose level. Dose reductions will not be allowed during the Dose Escalation Period. If a patient cannot be escalated to the next dose level, the patient will be discontinued from the study.

Maintenance Period (24 weeks, Visits 8 to 14 [Weeks 10 to 34])

Phase 2 and Phase 3 of the study

After completing the 3-week Dose Escalation Period, patients will enter the 24-week Maintenance Period.

[figure not shown]
Some patients may have their dose adjusted based on tolerability during the Maintenance Period.

After completion of the Maintenance Period, patients may be offered the opportunity to enroll in the long-term extension study (SCOUT-016). Patients who do not elect to enroll will be tapered off the IP.

[figure not shown]
Taper Period (14 days, Visit 14 [Week 34]) and Follow-up Period (14 days, Visits 15 and 16 [Weeks 36 and 38])

Patients who do not enroll in the long-term extension study (SCOUT-016) will have their IP tapered off over 14 days according to the following schedule: the IP should be decreased by 50% during the first 7 days, followed by an additional 50% during the following 7 days, and then discontinued. The taper schedule may be modified at the discretion of the Investigator but cannot be extended to a total period lasting more than 14 days. A final follow up will be conducted 2 weeks after the last dose of IP for patients who are tapered off.

A schematic representation of the Phase 2 and Phase 3 of the study is provided in the figures below:

* Patients assigned to placebo will include low, mid, and high volume placebo to match active drug and will be combined for statistical analysis.

Study Design Schematic – Phase 3 of the Study

*Patients assigned to placebo will be further broken down to achieve balanced exposure between placebo and RAD011 patients. The number of doses to be studied will be determined by the DMC's safety review.

Diagnosis and Main Criteria for Inclusion:

Inclusion criteria:

To be eligible for this study, patients must meet all of the following inclusion criteria:

1. Presence of a parent/legal guardian that is able to consent for their participation.
Parent/caregiver/legal guardian can complete the required assessments throughout the study. Patient Consent/Accent will be obtained if the patient is 8 years of age or older and has the mental capacity to understand and sign a written consent/assent form and/or give verbal assent
2. Males and females between:
 - a. Phase 2: 12 and 65 years of age (inclusive) at time of consent/assent
 - b. Phase 3: 8 and 65 years of age (inclusive) at time of consent/assent
3. Documentation of genetically confirmed PWS diagnosis

4. If a caregiver helps in completing the HQ-CT or other questionnaires, the same caregiver is available to complete the questionnaire throughout the duration of the study
5. If female, is either not of childbearing potential (defined as premenarchal or surgically sterile [bilateral tubal ligation, bilateral oophorectomy, or hysterectomy]) or practicing one of the following medically acceptable methods of birth control up to 4 weeks after the last dose of RAD011 or placebo:
 - a. Double barrier method (i.e., condom plus occlusive cap (diaphragm or cervical/vault caps), condom or occlusive cap plus spermicide)
 - b. Hormonal methods such as oral, implantable, injectable, vaginal ring, or transdermal contraceptives at a stable dose for a minimum of 1 full cycle (based on the patient's usual menstrual cycle period) before IP administration
 - c. Intrauterine device (IUD) or intrauterine hormone-releasing system (IUS)
 - d. If not using hormonal contraceptives or IUD or IUS, then all male partners throughout the study must have been vasectomized and have received medical assessment of the surgical success
6. If male, is vasectomized and has received medical assessment of the surgical success or agrees to use an approved method of contraception (double barrier method as described in **Inclusion Criterion 5**, female partner's use of an IUD or IUS [in place at least 12 weeks prior to dosing], oral contraceptives or female partner who is surgically sterile or 2 years postmenopausal) and agrees to use this method for 4 weeks after last administration of RAD011 or placebo
7. If receiving growth hormone (GH), psychotropic therapy, metabolic treatments that could affect appetite (including metformin), and other treatment including thyroid hormone, must be on the same medication and stable dose for at least 90 days prior to consent/assent
8. Any non-medical interventions (eg, counseling, behavior modification) should be stable for at least 90 days prior to consent/assent
9. HQ-CT eligibility automatically calculated in the electronic data capture (EDC) system:
 - a. Visit 2
 - i. Patients with a mean HQ-CT score ≥ 13 (from Visit 1 and Visit 2) will be eligible to continue in the Tolerability Period
 - b. Visit 5
 - i. Patients with a mean HQ-CT score ≥ 13 (from Visit 3, Visit 4 and Visit 5) will be eligible for randomization, and
 - ii. Patients with a decrease in HQ-CT score (from Tolerability Period to the Screening Period) ≤ 7 will be eligible for randomization

Exclusion criteria:

Patients meeting any of the following criteria will be excluded from the study:

1. Hypersensitivity or intolerance to CBD, or any other excipients used in the RAD011 preparation
2. Known use of cannabis or cannabinoid containing products (including topical products) within 90 days prior to consent/assent
3. History of chronic liver disease, such as cirrhosis or chronic hepatitis due to any cause
4. Positive urine test for drugs of abuse, including tetrahydrocannabinol (THC), or known history of drug, alcohol, or substance abuse

5. Use of prescription or over-the-counter weight loss agents within 90 days prior to consent/assent
6. Implementation of new food restrictions or environmental restrictions within 90 days of consent/assent
7. Any significant comorbid condition or disease:
 - a. Respiratory disease, heart disease, or psychiatric disorder which in the opinion of the Investigator would preclude the patient from participating or
 - b. Uncontrolled type 1 or type 2 diabetes as determined by the Investigator or
 - c. Clinically significant ECG abnormalities or other evidence of clinically significant heart disease as determined by the Investigator or
 - d. Uncontrolled sleep apnea as determined by the Investigator or
 - e. Neutropenia with neutrophil counts <1,000 /microL (grade 3 or grade 4 neutropenia as defined by CTCAE v5.0) or
 - f. History or presence of gastrointestinal disorders or any other condition known to interfere with the absorption, distribution, metabolism, or excretion of drugs taken orally as determined by the Investigator
8. QT interval corrected for heart rate (HR) according to Fridericia's formula (QTcF) meeting the following criteria:
 - a. For males and females aged 8 to <20 years: QTcF >439 msec
 - b. For males aged 20 to 65 years: QTcF >450 msec
 - c. For females aged 20 to 65 years; QTcF >470 msec
9. At consent/assent, patients with age-matched hypertensive levels of systolic and/or diastolic blood pressure may be excluded at the Investigator's discretion if deemed to be in the best interest of the patient.
10. Pregnant (determined by a positive serum pregnancy test) or lactating female
11. Unwillingness or inability to follow the procedures outlined in the protocol
12. Estimated glomerular filtration rate <30 mL/min/1.73m² or protein/creatinine ratio ≥0.4
13. Bilirubin >1.5 × upper limit of normal (ULN), or aspartate aminotransferase (AST), alanine aminotransferase (ALT) >3 × ULN, or international normalized ratio (INR) >1.5 × ULN
14. Patient judged by the Investigator or Sponsor (or designee) as unable to comply with the treatment protocol, including appropriate supportive care, follow up, and research tests
15. Other genetic, hormonal, chromosomal, cognitive, or behavioral impairment
16. If living in a group home, patient spends less than 25 waking hours with their caregiver per week.
17. Significant risk of committing suicide based on history, routine psychiatric examination, or based on the Investigator's judgment
18. Participation in any other study involving an investigational product or device within 4 weeks or 5 half-lives (whichever is longer) of consent/assent or longer as required by local regulations

Investigational Product, Dosage, and Mode of Administration:

RAD011 (Cannabidiol Oral Solution) 100 mg/mL, 10 mg/kg/day to 40 mg/kg/day, administered orally in two divided doses

Duration of Study Participation:

37 to 40 weeks

Reference Therapy, Dosage, and Mode of Administration:

Placebo (medium-chain triglyceride vehicle used in RAD011 formulation)

Criteria for Evaluation:Primary objective

The primary objective of the Phase 2 of this study is to assess the safety and tolerability of multiple doses levels of RAD011 in order to select 1 or 2 dose level(s) to further evaluate in the Phase 3 of the study.

The primary objective of the Phase 3 of this study is to assess the effect of RAD011 on hyperphagia-related behavior in patients with PWS.

Secondary objectives

The secondary objectives are to assess the following:

- Effect of RAD011 on irritability
- Effect of RAD011 on Clinician Global Impression of Change (CGI-C) in Hyperphagia
- Effect of RAD011 on Clinician Global Impression of Severity (CGI-S) of Hyperphagia
- Safety and tolerability of RAD011

Other objectives

The other objectives of this study are to assess the:

- Effect of RAD011 on Caregiver Global Impression of Change (CaGI-C) in Hyperphagia
- Effect of RAD011 on Caregiver Global Impression of Severity (CaGI-S) of Hyperphagia
- Effect of RAD011 on Caregiver Global Impression of Change (CaGI-C) in Irritability
- Effect of RAD011 on overall behavior
- Effect of RAD011 on sleep
- Effect of RAD011 on body mass index (BMI) and weight
- Effect of RAD011 on skin-picking behavior
- Effect of RAD011 on total muscle/fat composition (performed at selected United States [US] sites)

Endpoints:Primary efficacy endpoint:

- Change in HQ-CT scores from Baseline through End of Study/Week 34 Visit for RAD011 compared to placebo

Secondary efficacy endpoints:

- Change in PWS-associated Irritability from Baseline through End of Study/Week 34 Visit using the Aberrant Behavior Checklist (ABC) questionnaire – Irritability subscale (ABC-I) for RAD011 compared to placebo
- Change in hyperphagia as defined by the Clinician Global Impression of Change (CGI-C) in Hyperphagia through End of Study/Week 34 Visit
- Change in Clinician Global Impression of Severity (CGI-S) of Hyperphagia from Baseline through End of Study/Week 34 Visit

Other endpoints:

- Change in hyperphagia as defined by the Caregiver Global Impression of Change (CaGI-C) in Hyperphagia response through End of Study/Week 34 Visit for RAD011 compared to placebo

- Change in Caregiver Global Impression of Severity (CaGI-S) of Hyperphagia from Baseline through End of Study/Week 34 Visit
- Change in irritability as defined by the Caregiver Global Impression of Change (CaGI-C) in Irritability through End of Study/Week 34 Visit
- Change in overall behavior from Baseline through End of Study/Week 34 Visit using the ABC questionnaire subscales for RAD011 compared to placebo
- Change in sleep from Baseline through End of Study/Week 34 Visit using the Epworth Sleepiness Scale for Children and Adolescents (ESS-CHAD) for RAD011 compared to placebo
- Change in weight and BMI from Baseline through End of Study/Week 34 for RAD011 compared to placebo
- Change in skin picking behavior using the Skin Picking Questionnaire from Baseline through End of Study/Week 34 for RAD011 compared to placebo
- Change in muscle/fat composition using a dual-energy X-ray absorptiometry (DEXA) scan from Randomization through End of Study/Week 34 for RAD011 compared to placebo

Pharmacokinetic endpoints

Throughout the study, plasma samples will be collected to establish the PK profile of CBD and 2 metabolites, 7-OH-CBD and 7-COOH-CBD in patients with PWS. Furthermore, an exposure response analysis using CBD and 7-OH-CBD concentrations as well as a population PK model will be derived from the data.

Safety and Tolerability Endpoints:

Treatment-emergent adverse events, vital signs (blood pressure, HR, body temperature, respiratory rate, oxygen saturation), ECGs, and laboratory tests (chemistry, hematology, coagulation, and urinalysis)

Sample Size and Power Calculation:

DMC Recommendation of Two RAD011 Doses

For the primary efficacy analysis, a total of 150 patients (50 patients per treatment group) aged 12 to 65 years will provide 90% power to compare each dose group vs. placebo with a two-sided alpha of 0.025. The study is powered to detect a difference in the HQ-CT from Baseline to Week 34 of 5 points with a standard deviation of 7 points. The 0.05 Type 1 error is split equally between groups (low dose and high dose). The low- and high-volume placebo groups will be combined for all comparisons to placebo. Assuming a 15% post-randomization dropout rate, approximately 176 patients (~59 patients per treatment group) will be evaluated for the primary efficacy analysis.

Thus, if the DMC recommends two RAD011 doses for Phase 3 of the study, approximately a total of 191 patients (target approximately 200 patients) aged 12 to 65 years will be randomized in this study. The 191 reflects 176 patients required for primary efficacy analysis plus 15 patients randomized in the Phase 2 part of the study to the dose not selected for the Phase 3 part of the study.

Assuming a 20% pre-randomization eligibility failure rate (including HQ-CT eligibility criteria), approximately 240 patients will be enrolled in the Screening Period. An additional 10 patients per treatment group aged 8 to <12 years may be allowed to participate in the Phase 3 part of the study and will be randomized in a way to obtain a balanced number of patients on RAD011 (at dose levels recommended by the DMC) and placebo. Patients aged 8 to <12 will not be included in the primary efficacy analysis.

DMC Recommendation of One RAD011 Dose

For the primary efficacy analysis, a total of 100 patients (50 patients per treatment group) aged 12 to 65 years will provide 94% power to compare active vs. placebo with a two-sided alpha of 0.05. The study is powered to detect a difference in the HQ-CT from Baseline to Week 34 of 5 points with a standard deviation of 7 points. Assuming a 15% post-randomization dropout rate, approximately 118 patients (~59 patients per treatment group) will be evaluated for the primary efficacy analysis.

Thus, if the DMC recommends one RAD011 dose for the Phase 3 part of the study, approximately 148 patients (target approximately 150 patients) aged 12 to 65 years will be randomized in this study. The 148 reflects 118 patients required for primary efficacy analysis plus 30 patients randomized in the Phase 2 part of the study to the two doses not selected for the Phase 3 part of the study.

Assuming a 20% pre-randomization eligibility failure rate (including HQ-CT eligibility criteria), approximately 185 patients will be enrolled into the Screening Period. An additional 10 patients per treatment group aged 8 to <12 years may be allowed to participate in the Phase 3 part of the study and will be randomized in a way to obtain a balanced number of patients on RAD011 (at dose level recommended by the DMC) and placebo. Patients aged 8 to <12 will not be included in the primary efficacy analysis.

Statistical Methods:Analysis Populations:

The following patient populations will be defined for analysis:

- Safety Population: the Safety Population will include all randomized patients who were treated with at least one dose of IP
- Intent-to-Treat (ITT) Population: the ITT Population will include all randomized patients
- Modified ITT (mITT) Population: the mITT Population will include all patients aged ≥ 12 years who were randomized, received at least 1 dose of IP, had at least 1 post-randomization HQ-CT questionnaire completed, and were randomized to receive the dose level(s) recommended for development in the Phase 3 part of the study, including patients in the Phase 2 part of the study who received the chosen dose level(s)
- Per Protocol (PP) Population: the PP Population will include all patients aged ≥ 12 years who were randomized, received at least 1 dose of IP, completed Week 34 without significant protocol deviations that were prospectively defined to impact efficacy (see SAP) and received the dose level(s) recommended for development in the Phase 3 part of the study, including patients in Phase 2 of the study who received the chosen dose level(s)
- Pharmacokinetic (PK) Evaluable Population: the PK Evaluable Population will include all patients who received at least 1 dose of IP and underwent at least 1 PK sample collection.

Efficacy Analyses:

The primary endpoint, change in HQ-CT score from Baseline to End of Study (Week 34), will be analyzed for the mITT population based on the treatment policy estimand using a mixed model for repeated measures (MMRM) with change in HQ-CT score as the response variable and randomization assignment, Baseline HQ-CT score and stratification variables (age [≥ 16 or <16 years] at randomization and GH treatment at randomization [yes/no]) and time \times treatment interaction as fixed effects. Patient will be included as a random effect with an unstructured covariance matrix. A multiple imputation will be used for missing data. Baseline will be defined as the mean HQ-CT score (Visit 1, Visit 2).

DMC Recommendation of two RAD011 Doses

The primary comparison will be mean change in HQ-CT as calculated via least square means comparing RAD011 low dose vs. placebo and RAD011 high dose vs. placebo at Week 34. Low dose and high dose groups will be compared to placebo at the two-sided 0.025 level so overall Type 1 error is maintained at two-sided 0.05 level.

DMC Recommendation of one RAD011 Dose

The primary comparison will be mean change in HQ-CT as calculated via least square means comparing RAD011 vs. placebo at Week 34. RAD011 will be compared to placebo at the two-sided 0.05 level.

Pharmacokinetic Analyses:

All PK analyses will be described in the pharmacokinetic analysis plan prior to performing statistical analyses. A pharmacodynamic analysis may be completed to evaluate exposure with efficacy and safety.

Safety Analyses:

The Safety Population will be used for all safety assessments. Safety assessments will be based on adverse events (AEs), Columbia-Suicide Severity Rating Scale (C-SSRS), vital signs, ECGs, and laboratory assessments. All analyses of safety will be described in the Statistical Analysis Plan (SAP).

All safety assessments will be descriptive, and no inferential statistics will be performed. All data listings will be provided for protocol specified safety data. The Medical Dictionary for Regulatory Activities will be used to classify all AEs with respect to System Organ Class (SOC) and preferred term. Adverse event summaries will include only treatment-emergent adverse events (TEAEs) by treatment group. Assessment of severity and relationship will also be presented. Adverse events leading to study discontinuation will also be summarized by SOC, Preferred Term, severity, and relationship.

The C-SSRS will be used to evaluate suicidal ideation and intensity of ideation. Ideation and intensity will be grouped by categories, with separate groupings for the Baseline/Screening and the “Since Last Visit” questionnaires.

Clinical laboratory and vital signs will be summarized for the Safety Population for observed values and change from Baseline. Shifts from Baseline according to normal range criteria will also be presented for all patients in the Safety Population.

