11.4.2. Primary Endpoint

The primary endpoint, change in HQCT score from Baseline to End of Study (Week 34) will be analyzed for the mITT population based on the treatment policy estimand using a mixed model for repeated measures (MMRM) with change in HQCT score as the response variable and randomization assignment, Baseline HQ-CT score and stratification variables (age [≥ 16 or < 16 years] at randomization and GH treatment at randomization [yes/no]) and time \times treatment interaction as fixed effects. Patient will be included as a random effect with an unstructured covariance matrix. A multiple imputation will be used for missing data. Baseline will be defined as the mean HQ-CT score (Visit 1, Visit 2).

For the primary endpoint analysis at Week 34, multiple imputation will be used to assign a value to those cases with missing data. The full conditional specification method with predictive means matching as described in Berglund & Heeringa ([Berglund, 2014](#)) will be used. This method uses all of a patient's known primary outcome measures at Baseline, Weeks 10, 19, 27, and/or 34 weeks to impute any missing values for Week 34.

DMC Recommendation of two RAD011 Doses

The primary comparison will be mean change in HQ-CT as calculated via least square means comparing RAD011 low dose vs. placebo and RAD011 high dose vs. placebo at Week 34. Low dose and high dose groups will be compared to placebo at the two-sided 0.025 level so overall type 1 error is maintained at two-sided 0.05 level.

DMC Recommendation of one RAD011 Dose

The primary comparison will be mean change in HQ-CT as calculated via least square means comparing RAD011 vs. placebo at Week 34. RAD011 will be compared to placebo at the two-sided 0.05 level.

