11.4.3. Secondary and Other Endpoints

All analyses of the secondary and other endpoints for continuous measures will be conducted analogous to the primary endpoint analysis, using, the baseline value of the relevant variable as a

covariate, and patient as a random effect. All analyses of the secondary and other endpoints will be described in the SAP.

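### The primary MMRM gives Baseline HQ-CT one slope for all visits; adding Baseline × time would protect precision at Week 34 at almost no cost

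*Protocol*

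**What the plan says.** The Synopsis (Statistical Methods, Efficacy Analyses) defines the primary MMRM "with change in HQ-CT score as the response variable and randomization assignment, Baseline HQ-CT score and stratification variables", the strata being age (16 or over versus under 16) and growth hormone treatment. The list closes with time × "treatment interaction as fixed effects". Section 11.4.2 repeats the specification: "with change in HQCT score as the response variable and randomization assignment, Baseline HQ-CT score and stratification variables". Neither place has a baseline × time term, and neither names time as an effect of its own.

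Other relevant statements:
- Covariance: "Patient will be included as a random effect with an unstructured covariance matrix".
- Baseline: "Baseline will be defined as the mean HQ-CT score (Visit 1, Visit 2").
- Visits, from the imputation text in Section 11.4.2: all of a patient's "known primary outcome measures at Baseline, Weeks 10, 19, 27, and/or 34 weeks to impute any missing values for Week 34".
- Primary contrast if two doses go forward: least-squares means "comparing RAD011 low dose vs. placebo and RAD011 high dose vs. placebo at Week 34". With one dose it is likewise at Week 34.
- Section 11.4.3: continuous secondary and other endpoints are "conducted analogous to the primary endpoint analysis, using, the baseline value of the relevant variable as a" covariate, with their analyses left to the SAP.

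**The concern.** Treatment may vary with time in this model, but the baseline slope may not. Fitted as written, the model estimates one slope from four visits and uses it to adjust a contrast at one of them. If the true slope differs by visit, the Week 34 adjustment uses the wrong slope. Randomization keeps the contrast unbiased, but the misfit adds to the Week 34 residual variance.

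A changing slope is plausible. On the schedule in Tables 6 and 7, Visit 2 is Day 1, Week 10 is Day 64 and Week 34 is Day 232, so the lag from Visit 2 grows from 63 days (9 weeks) to 231 days (33 weeks). Section 5.2 acknowledges variability in hyperphagia and in HQ-CT responses. What is at stake is efficiency in the primary comparison and, through Section 11.4.3, in continuous endpoints measured at several visits.

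**Working it through.** **1. The plan's own figures.** Inputs from the Synopsis and Section 11.1: difference 5, SD 7, 50 per group, 15% dropout.
- Two-sided 0.025: 5 / (7 × √(2/50)) = 3.571; Φ(3.571 − 2.241) = 0.908, or 0.900 with the noncentral t. Stated: 90%.
- Two-sided 0.05: Φ(3.571 − 1.960) = 0.946, or 0.943. Stated: 94%.
- Dropout: 150/0.85 = 176.5 and 100/0.85 = 117.6. Stated: 176 and 118.

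All reproduce.

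**2. Formula.** Let r_t be the correlation of baseline with the score at visit t, and take equal score SDs across visits. With an unstructured covariance, complete data and treatment free at each visit, the common slope is a weighted mean of the four visit slopes. The weights w are proportional to S⁻¹1, where S is the visit covariance given baseline. With r_w = Σ w_t r_t:

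Week 34 variance, common slope ÷ visit-specific slope = 1 + (r_34 − r_w)² / (1 − r_34²)

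The baseline SD cancels.

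**3. Results.** The protocol gives no correlations, so all of these are assumed. Each range covers two between-visit structures: exchangeable 0.7 and first-order autoregressive 0.85.

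| r at Weeks 10, 19, 27, 34 | Weight on Week 34 | Variance ratio | SE |
|---|---|---|---|
| Flat: 0.50 throughout | 0.25 to 0.43 | 1.000 | +0.0% |
| Mild: 0.60, 0.57, 0.53, 0.50 | 0.16 to 0.37 | 1.004–1.005 | +0.2% |
| Moderate: 0.65, 0.58, 0.52, 0.45 | 0.05 to 0.28 | 1.021–1.026 | +1.1 to 1.3% |
| Steep: 0.70, 0.58, 0.46, 0.35 | −0.14 to 0.17 | 1.085–1.122 | +4.2 to 5.9% |

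Example (steep, exchangeable): weights 0.65, 0.38, 0.11, −0.14 give r_w = 0.677, and (0.35 − 0.677)² / (1 − 0.35²) = 0.107/0.8775 = 0.122.

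**4. Simulation** (4,000 trials per pattern, 50 per arm, complete data). Empirical Week 34 SE, visit-specific versus common slope, exchangeable structure:
- Flat: 1.414 vs 1.412.
- Mild: 1.391 vs 1.392.
- Moderate: 1.416 vs 1.435, variance ratio 1.027.
- Steep: 1.381 vs 1.468, variance ratio 1.130.

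Both estimators averaged between −4.98 and −5.02 for a true −5. A second simulation (59 per arm, between-visit correlations about 0.6–0.75) gave ratios of 1.009–1.012 for a fall from 0.60 to 0.40–0.45, and 1.067–1.071 for a fall from 0.70 to 0.35–0.40.

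**5. Cost of the extra term when slopes are flat.** Model-based SE 1.402 versus 1.396: (1.402/1.396)² = 1.009, or about 0.9% of variance.

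**6. Power in the steep case.** Take a Week 34 score SD of 7.
- Visit-specific residual SD: 7 × √(1 − 0.35²) = 6.56.
- Common slope: 6.56 × √1.085 = 6.83 to 6.56 × √1.122 = 6.95, still below 7.
- Power at 50 per arm and two-sided 0.025: 0.942 with the interaction, 0.913–0.922 without.

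**The case against.** **The list may be shorthand.** Section 11 leaves statistical detail to the SAP, and the list omits even the time effect that any MMRM needs. The missing interaction therefore cannot be read as a deliberate exclusion. That is fair. Still, the protocol names the covariates, the interaction and the covariance structure, and an analyst who follows it fits a single slope.

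**Decay is not demonstrated.** Baseline is already 9 to 12 weeks old at Week 10, so much of any loss of correlation may come before the first modelled visit. General variability in HQ-CT responses weakens the slope at every visit and does not show that it changes. This stands: decay is an assumption.

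**A reader might infer that the trial falls below its stated 90% power.** Holding the residual SD after adjustment at 7, the steep case gives power of 0.871–0.882. The protocol, however, attaches SD 7 to the change from Baseline to Week 34 and claims no credit for covariate adjustment. Step 6 stays below 7. If 7 is instead the unadjusted change SD, the outcome depends on the baseline SD, which is not given. In the worse steep case, a baseline SD of 5 makes the unadjusted change SD √(49 + 25 − 2 × 0.35 × 35) = 7.04, and the common-slope SD rescales to 6.95 × 7/7.04 = 6.91. With a baseline SD of 4 the figures are √(49 + 16 − 2 × 0.35 × 28) = 6.74 and 7.22. The documents do not establish a shortfall.

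**A reader might also infer bias or inflated Type I error.** Neither follows: under randomization a mis-sloped covariate costs precision only.

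**Secondary endpoints.** Section 11.4.3 defers these to the SAP. CGI-C is collected only at Week 34 (Section 5.8.5.1, Table 7), so the term cannot apply to it.

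**Conclusion.** The point holds as a minor matter of efficiency. As written, one baseline slope serves four visits while only Week 34 is tested. The excess Week 34 variance is nil if the baseline relation is constant, about 0.5–3% for mild to moderate decay, and about 7–12% for a steep fall from 0.70 to 0.35–0.38. At 59 per arm, 7–12% is worth about 59 × (1 − 1/1.07) = 4 to 59 × (1 − 1/1.12) = 6 patients per arm. These sizes rest on assumed correlations, equal SDs across visits and complete data. They illustrate the effect and do not bound it, since a still steeper fall would cost more. A main-effect baseline covariate is a legitimate choice; the case for change is that the possible gain exceeds the possible loss.

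**What to change.** In the Synopsis and Section 11.4.2, name time as a fixed effect and add Baseline HQ-CT × time. This replaces one slope with four, so it adds three parameters. It needs no new data and costs at most about 1% of variance if the slope is in fact constant. Because Section 11.4.3 makes the continuous secondary and other analyses analogous, let each such endpoint measured at several visits use its own baseline × time term, with the detail in the SAP. Endpoints collected only at Week 34 need no change.
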